10.4 Reporting Urgent Safety Measures

If any urgent safety measures (USM) are taken, the CI/delegate shall immediately, give written notice to the Sponsor and the relevant REC of the measures taken and the circumstances giving rise to those measures. The CI/delegate must inform all Principal Investigators at participating sites of the USM immediately, or within 3 days from the date the measures were taken. The CI/delegate will document this in accordance with the University of Leicester's SOP for Urgent Safety Measures.

11. STATISTICS AND DATA ANALYSIS

11.1 Sample size calculation

No minimal clinically important difference (MCID) has been reported for muscle strength as determined by isometric dynamometry in the CKD population. However, our data have shown that a 10Nm increase in muscle strength was associated with a reduction in 3-year mortality of 5% (54). The data we have used in our sample size calculation come from the improvement in strength that has been previously reported by three previous studies of NMES in haemodialysis patients (27, 30, 33) i.e. a mean strength improvements of 21.7Nm and a mean standard deviation of 47.5Nm. A total sample size of 228 participants (114 per arm) is needed to detect a 21.7Nm (SD 47.5Nm) difference (standardised effect size of 0.5 (moderate)) in change in muscle strength between groups at 3-months with 90% power at the 5% significance level. This will also account for an expected 10% total attrition rate, based on our previous data (15).

11.2 Planned recruitment rate

[name] are both established investigators within their NHS Trusts; all proposed dialysis units fall in the governance of NHS Trusts where they are clinical leads. As the Chief Investigator of the CYCLE-HD study, [name] oversaw recruitment of 130 participants to a 6-month dialysis-based exercise study (using cardiac MRI) at a recruitment rate of 1-2 participants per week across 3 units. Given that the intervention was more complex and of longer duration, with outcome measures more onerous to collect, we believe a recruitment rate of 2-4 participants per week over 21-months is achievable and will comfortably exceed our required sample size of 228.

11.3 Statistical analysis plan

A statistical analysis plan (SAP) will be prepared by the Trial Statisticians and will contain full details of all statistical analyses. The SAP will be agreed with appropriate oversight prior to database lock and published in a study protocol paper. Any changes to the original SAP will be detailed along with the reason(s) for changes in subsequent SAPs. No formal stopping rules or interim analyses have been pre-defined or planned.

11.3.1 Summary of baseline data and flow of participants

Some, or all of the following baseline data will be collected from all participants:

- Demographic information (e.g. height, weight, date of birth, ethnicity, gender)
- Clinical information (e.g. prescriptions, comorbidities, haemoglobin, glucose, hba1c, eGFR, creatinine, WBC, Fev1)
- Isometric strength (N)
- Rectus femoris cross-sectional area (cm²)
- Fat mass (kg)

- Fat free mass (kg)
- Lean body mass (kg)
- Body fat (%)
- Skeletal muscle mass (kg)
- Appendicular lean mass (kg)
- Muscle thickness (mm)
- Angle of pennation (degrees)
- Distance covered during the 6-minute walk test (m)
- Hand grip strength (kg)
- Sit to stand 5 (secs)
- Sit to stand 60 (repetitions)
- Balance (seconds)
- Gait speed (m/s)
- KDQoL (points)
- GP-PAQ (points)
- ED-5D-5L (points)
- SARC-F (points)
- SONG-HD-fatigue (points)
- SarQoL (points)
- Motor unit recruitment and decruitment threshold (Nm)
- Motor unit discharge frequency (Hz)
- Motor unit conduction velocity (m/s)
- Motor unit potential jiggle and segment jitter (AU)
- Quadriceps twitch contractile properties (Nm)
- Quadriceps maximal M-wave (mV)

Plasma/serum samples will be analysed/used for all or some of:

- Markers of muscle metabolism/homeostasis
- Inflammatory markers and immune function/activation
- Biomarkers of cardiovascular risk
- Endothelial damage
- Oxidative stress
- Anabolic/catabolic hormones
- microRNA expression
- Exosome/micropartical isolation
- Genetic analysis

Skeletal muscle biopsy samples will be analysed for all or some of:

- Markers of muscle metabolism/homeostasis
- Muscle morphology/architecture/fibre type
- Protein turnover (protein synthesis and degradation) and events leading to this
- The process of myogenesis (muscle repair and regeneration)
- Intramuscular inflammation and processes relating to this
- Mitochondria number/function and processes relating to this
- Amino acid content and transport
- RNA and microRNA expression

11.3.2 Descriptive analysis

Data will be checked for outliers and missing values and validated using the defined score ranges for all outcome measures. Baseline data will be summarised by group to assess comparability between treatment arms, and to highlight any characteristic differences. Statistical tests for imbalance will not be carried out.

It is likely that some data may not be available due to death, kidney transplantation, and voluntary withdrawal of participants or lack of completion of individual data items. Where possible the reasons for missing data will be ascertained and reported. Although every effort will be made to minimise crossovers from both intervention arms, the numbers, direction and reasons for participants moving between arms will be recorded and reported in line with CONSORT (Consolidated Standards of Reporting Trials) guidance.

11.3.3 Analysis of primary outcome

The primary analysis will compare the change in muscle strength from baseline to 3-months (i.e. at the end of the intervention period) between randomised groups. The primary analysis will be conducted by intention to treat (ITT) comparing all those randomised to the NMES programme to those who were randomised to standard care. Linear regression with change in muscular strength as the dependent variable, adjusted for baseline value and the minimisation factors (age, time on dialysis), will be used to compare treatment groups, the adjusted mean difference between the treatment arms will be presented with a 95% confidence interval.

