3.3 Outcome measures/endpoints

3.3.1 Primary endpoint/outcome

Primary Endpoint: The primary outcome is change in muscle strength measured using isometric dynamometry from baseline to 3-months.

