6. PARTICIPANT ELIGIBILITY CRITERIA

6.1 Inclusion criteria

- 1. Undertaking HD for >3-months (home or unit based)
- 2. Age >18 years
- 3. Has sarcopenia diagnosed by low muscle strength on patient screening (<27kg for men and <16kg for women for handgrip strength)
- 4. Able to give written informed consent

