8.6 Randomisation

After consent and baseline measurements have been collected, participants will be randomised by a delegated individual at each participating centre to either the intervention (3-months of NMES) or the control group (standard care) in a 1:1 manner. Participants will be allocated using minimisation factors of age and time on dialysis, this will ensure the external validity of the results.

Each participant will be given a unique participant ID number at randomisation. This participant ID number will be used to identify the individual participant throughout the study and will not be re-assigned to any other participant. Due to the nature of the intervention, blinding of the participants and the study team to the randomisation arm is not possible.

Randomisation will be performed using a validated web-based system to maintain allocation concealment. This will be managed by the Leicester Clinical Trials Unit.

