8.7 Baseline data

These assessments can be split over multiple visits if the participant wishes.

1) Demographic and clinical information:

Date of birth/age, gender at birth, ethnicity, medical history and medications will be collected from hospital records.

2) Hand Grip Strength

Participants will perform this assessment seated with their feet flat on the floor, or standing if participant cannot be seated using the non-fistula arm. Participants will be asked to squeeze the handheld dynamometer as hard as they can on three occasions with a short rest in between. The highest measurement will be taken.

3) Isometric strength and rate of force development

Participants will be seated in a custom-built dynamometer, with their lower leg secured to a brace in series with a strain gauge force transducer. Following a series of warm-up contractions of gradually increasing force, participants will perform a series of 3-4 brief maximum voluntary contractions lasting ~5 s and separated by ~1 minute of rest, attempting to exert as much force as possible during each contraction. After that, participants will perform 10 efforts of contracting "as fast and as hard as possible" for ~1 s to at least 80% of maximal force (separated by 30-45 seconds of rest) to allow assessments of the rate of force development.

4) Quadriceps Cross-sectional area and architecture

Measures will be taken at mid-point of the thigh, and three measures (within 10%) of rectus femoris cross sectional area will be taken and the mean recorded. Three measures of muscle thickness will be taken and the mean recorded. Images of the quadriceps will be taken (pseudonymised) for later analysis of grayscale (muscle quality). Muscle thickness and angle of pennation will also be measured by ultrasound at points along the quadricep.

5) Short Physical Performance Battery

This involves 3 successive balance tests, side by side stand, semi tandem stand, and full tandem stand, a gait speed test and sit to stand 5 test.

Balance tests

The participant is asked to stand unsupported for 10 seconds with their feet in a certain position (feet together, semi tandem, full tandem). The length of time they are able to remain balanced for in seconds is recorded.

Figure 2: Image of three foot positions during the balance tests

Gait Speed

The participant walks between two timing gates or cones at their usual walking pace placed 4m apart. Speed in m/s is recorded.

Sit to Stand 5 test

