11.4. Subgroup analyses

A priori sub group analysis will include, gender, age, time on dialysis, physical activity levels (i.e. sedentary versus active) and the severity of sarcopenia at baseline (i.e. probable vs severe).

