11.5 Adjusted analyses

The primary analysis will be adjusted for the minimisation factors.

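### Adding sex to the primary strength model would give a small, nearly free gain in precision; the planned model is valid without it

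*Protocol*

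**What the plan says.** All references are to the main trial protocol, not the Work Package 1 pilot.

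- **Outcome.** Section 3.3.1 defines it as "change in muscle strength measured using isometric dynamometry from baseline to 3-months".
- **Model.** Section 11.3.3 specifies linear regression of change in strength, "adjusted for baseline value and the minimisation factors (age, time on dialysis"). Section 11.5 adds: "The primary analysis will be adjusted for the minimisation factors".
- **Allocation.** Section 8.6: "Participants will be allocated using minimisation factors of age and time on dialysis".
- **Where sex does appear.** Section 8.7 collects it: "Date of birth/age, gender at birth, ethnicity, medical history and medications will be collected from hospital records". Section 6.1 sets sex-specific screening limits ("<27kg for men and <16kg for women for handgrip strength"). Section 11.4 lists it as a subgroup: "A priori sub group analysis will include, gender, age, time on dialysis".
- **Secondary outcomes.** Section 11.3.4 has them analysed in a similar way to the primary outcome.
- **Sample size.** Section 11.1 uses "a mean strength improvements of 21.7Nm and a mean standard deviation of 47.5Nm", 90% power, 5% significance and 10% attrition to reach 228. It claims no gain from covariates.

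**The concern.** Men and women differ in average strength, and this protocol treats them as different when it screens on grip. Baseline strength carries most of that information into the model, but not all of it. A single strength reading is imperfectly reliable, so a follow-up value tends to regress towards the mean of the participant's own sex. A man and a woman with the same baseline reading then have different expected 3-month values. A model without sex leaves that difference in the residual.

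Two modest things are at stake. The confidence interval is slightly wider than it need be. A chance difference between arms in the share of men, which minimisation on age and time on dialysis does not control, is corrected only in part through baseline strength.

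The protocol names a specific covariate list in 11.3.3 and 11.5. The point is therefore about a choice already made, and not about detail left to the statistical analysis plan.

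**Working it through.** **1. Reproduce the plan's figure.** The standardised difference is 21.7/47.5 = 0.457. With 90% power and two-sided 5% (the protocol does not state sidedness, but two-sided reproduces its figure), the exact t calculation needs 102 per arm. Then 102/0.9 = 113.3, rounded up to 114 per arm, 228 in total. The normal approximation gives 101 per arm and 226 in total. The stated 228 is reproduced with no allowance for sex. Expected completers are 228 × 0.9 = 205.2, or 102.6 per arm, at which exact-t power is 90.3%.

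**2. Residual variance with and without sex.** Set the within-sex variance of strength to 1 at both times. Let *k* be the between-sex variance and *r* the within-sex correlation between baseline and 3 months, with the sex gap equal at both times. Because baseline is a covariate, modelling change or the 3-month value gives the same residual.

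- Without sex, the baseline slope is b = (r + k)/(1 + k) and the residual variance is (1 − r)(1 + r + 2k)/(1 + k).
- With sex, the residual variance is (1 − r)(1 + r).
- The ratio is (1 + r + 2k)/[(1 + k)(1 + r)], which exceeds 1 whenever k > 0 and r < 1.

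Neither *k* nor *r* is in the documents. The ranges below are assumptions.

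| k, r | Ratio | Variance cut | Worth in completers, 205 × (ratio − 1) |
|---|---|---|---|
| 0.10, 0.85 | 2.05/2.035 = 1.007 | 0.7% | about 2 |
| 0.25, 0.75 | 2.25/2.1875 = 1.029 | 2.8% | about 6 |
| 0.50, 0.60 | 2.60/2.40 = 1.083 | 7.7% | about 17 |

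**3. Power at 102.6 per arm (exact t), under two readings of 47.5 Nm.**

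*Reading A: 47.5 Nm is the residual SD of the planned model.* Adding sex multiplies the standardised difference by the square root of the ratio.

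*Reading B: 47.5 Nm is the SD of unadjusted change.* The variance of change is 2(1 − r), since the sex gap cancels. As a share of it, the planned model leaves (1 + r + 2k)/[2(1 + k)], and the model with sex leaves (1 + r)/2.

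| k, r | A: planned → with sex | B: planned → with sex |
|---|---|---|
| 0.10, 0.85 | 90.3% → 90.5% | 92.1% → 92.3% |
| 0.25, 0.75 | 90.3% → 91.0% | 93.0% → 93.6% |
| 0.50, 0.60 | 90.3% → 92.4% | 93.8% → 95.4% |

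The gain is about 0.2 to 2 points under A and 0.2 to 1.6 points under B.

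**4. Chance imbalance in sex.** Assume 60% men and ignore any indirect balancing through the minimisation factors. The between-arm difference in the share of men has SD √(0.6 × 0.4 × 2/114) = 0.065, so a difference above 10 points has probability about 0.12. With 102.6 completers per arm the SD is 0.068 and the probability about 0.14.

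**5. What baseline adjustment leaves behind.** The leftover shift is (1 − b) × sex gap × imbalance. At k = 0.25 and r = 0.75, b = 1.00/1.25 = 0.80. For an assumed gap of 30 to 50 Nm and a 10-point imbalance, this is 0.20 × 30 × 0.10 = 0.6 Nm to 0.20 × 50 × 0.10 = 1.0 Nm, or about 3 to 5% of 21.7 Nm.

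A second set of assumptions gives a similar scale. With a within-sex SD of 47.5 Nm and a gap of 0.5 to 1.5 SD, the leftover is about 0.2 to 1.4 Nm for r of 0.7 to 0.9, and at most about 2.3 Nm at r = 0.5.

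**The case against.** The strongest reply is that nothing here is wrong. Sections 8.6, 11.3.3 and 11.5 agree with each other, and adjusting for baseline value and the minimisation factors is standard. The estimate is unbiased under randomisation, and its confidence interval already allows for chance imbalance. Any prognostic variable left out of a model is only partly corrected for. The target power is met without sex, and every input to the size of the gain is assumed. All of this stands, and it limits the point to an improvement.

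A reader might infer more from the documents in four ways that they do not support.

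- **That the primary analysis is biased or underpowered.** It is neither: 228 is reproduced with no covariate gain.
- **That the 27 kg and 16 kg limits show how far sex predicts the outcome.** They are handgrip screening thresholds. The outcome is change in isometric leg strength, adjusted for its own baseline, and the documents give no leg strength by sex. The limits make a sex effect plausible but do not measure it.
- **That the planned gender subgroup forces sex into the primary model.** It does not. Physical activity and sarcopenia severity are also listed in 11.4 and are not primary covariates.
- **That every secondary model needs sex.** The argument concerns muscle strength and, by extension, muscle size. It gives no reason to change the models for quality of life, fatigue or other questionnaires.

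What the reply does not remove is that a recorded and probably prognostic variable can be used at almost no cost.

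**Conclusion.** The point holds as a small precision gain for strength outcomes. Under the assumed ranges (*k* 0.1 to 0.5, *r* 0.60 to 0.85), residual variance falls by about 0.7 to 7.7%, and power rises by about 0.2 to 2 points, or by 0.2 to 1.6 points if 47.5 Nm describes unadjusted change. For a 10-point sex imbalance, the shift left uncorrected is about 0.6 to 1.0 Nm, on an assumed gap of 30 to 50 Nm with *k* = 0.25 and *r* = 0.75.

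The direction is sound provided that sex predicts 3-month strength beyond baseline, age and time on dialysis. That is likely, but the documents do not show it. If sex adds nothing, the loss is one degree of freedom. The matter is optional, and no conclusion of the trial depends on it.

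**What to change.** - In 11.3.3 and 11.5, prespecify sex as a fixed covariate in the primary model, alongside baseline value, age and time on dialysis.
- In 11.3.4, do the same for the strength and muscle-size secondary outcomes, such as handgrip strength, rectus femoris cross-sectional area and muscle thickness.
- Leave the minimisation scheme, the sample size and the models for questionnaire outcomes unchanged.

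The cost is a short wording change and one degree of freedom per model, with no new data, visits or participants. It is best made now: section 8.6 says the study team cannot be blinded to allocation, and section 11.3 requires the analysis plan to be agreed only before database lock. A covariate named early cannot be questioned as chosen with the data in view.

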11.3.4 Analyses of secondary outcomes

The secondary outcomes will be analysed in a similar manner to the primary outcome. All represent continuous data and therefore linear regression will be used. All analyses will be adjusted for baseline value and the stratification factors. The number of deaths and cardiovascular events expected is relatively low, therefore formal time to event analyses will not be conducted. Kaplan–Meier will be presented to describe the relationship between these events and treatment.

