3.3.2 Secondary endpoints/outcomes

Secondary endpoints:

To compare between randomised groups;

- 1. Additional efficacy measures
 - a. Muscle size and architecture (measured cross-sectional area of rectus femoris using ultrasound, muscle thickness and angle of fibre pennation)
 - b. Lower-extremity strength, functional capacity, and balance: The short physical performance battery (SPPB)
 - c. Cardiovascular functional capacity and endurance: the 6-minute walk test (or incremental shuttle walk test in the event of space constraints)
 - d. Body composition (including lean muscle mass) using bioelectrical impedance
 - e. Sit-to-stand-60 test (muscle endurance)
 - f. GP Physical Activity questionnaire
 - g. Hand Grip strength
 - h. Accelerometry and sleep diary
 - i. Isometric rate of force development
- 2. Measures of QoL and social functioning
 - a. The Kidney Disease Quality of Life tool (KDQoL)
 - b. EQ-5D-5L, a generic multi-attribute health related QOL questionnaire for use in cost utility analysis (health economic analysis).
 - c. Levels of fatigue (using SONG-HD score)
 - d. SARC-F (validated questionnaire recommended as the screening instrument for sarcopenia in clinical practice by the European Working Group)
 - e. Sarcopenia and quality of life (SarQoL questionnaire)
- 3. NHS Resource use (collected via participant self-completion questionnaire), to be combined with NHS unit costs for use in cost utility analysis
- 4. Measures of process and tolerability
 - a. Number of patients eligible, approached and recruited
 - b. Dropout rates and movement between allocated study groups
 - c. Tolerability of the intervention to include number of neuromuscular stimulation sessions undertaken and the total time per session (up to 30-minutes).
- 5. Measures of safety
 - a. Adverse events relating to the intervention
- Measures of neuromuscular adaptations and muscle phenotype
 - High-density surfacer electromyography, for assessment of quadriceps motor unit recruitment and discharge rate, and conduction velocity during sub-maximum and maximum knee extension contractions.

- b. Intramuscular electromyography, for assessment of motor unit potential jiggle and segment jitter, electrophysiological markers of neuromuscular junction transmission stability.
- c. Femoral nerve stimulation, for assessment of quadriceps contractile properties.
- d. Skeletal muscle biopsy analysis

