3.4 Table of endpoints/outcomes

Objectives	Outcome Measures	Timepoint(s) of evaluation of this outcome measure (if applicable)
Primary Objective: To measure the effect of a 3-month NMES programme on muscle strength, the core manifestation of sarcopenia, compared with standard care for HD patients	Isometric strength	Screening visit (as a familiarisation session), baseline, 3, 6, 9 months post randomisation
Secondary Objectives To measure the effect of a NMES programme on QoL	The Kidney Disease Quality of Life tool (KDQoL)	Baseline, 3, 6, 9 months post randomisation
To evaluate the cost-effectiveness of a NMES programme compared with standard care for patients with end-stage kidney disease within an NHS costing perspective – health economic evaluation	EQ-5D-5L questionnaire Resource use questionnaire	Baseline, 3, 6, 9 months post randomisation
To measure the effect of a NMES programme on muscle size and measures of physical function	Muscle mass (thickness and cross- sectional area by ultrasound) Muscle quality and architecture (e.g. echo intensity and angle of pennation by ultrasound)	Baseline, 3, 6, 9 months post randomisation
	Handgrip strength by dynamometry	
	Lower-extremity strength, functional capacity, and balance (using the short physical performance battery (SPPB)) and Sit to stand 60.	
	Cardiovascular functional capacity and endurance (by the 6-minute walk test or the ISWT if space constraints)	
	Body composition (using bioelectrical impedance)	
	Muscle endurance (using the Sit-to- stand-60 test muscle endurance)	
	Isometric rate of force development	
	Physical activity levels (using GP Physical Activity questionnaire and accelerometry)	

To investigate if NMES results in neuromuscular adaptations and changes in muscle phenotype	Levels of fatigue (using SONG-HD score) Perception of muscle function (using the SarQoL questionnaire) Indices of sarcopenia (using the SARC-F questionnaire). Motor unit recruitment, and discharge rate, and conduction velocity (using high density electromyography) Motor unit potential jiggle and segment jitter (using intramuscular electromyography) Evoked quadriceps contractile properties Skeletal muscle biopsy analysis	Baseline, 3-months post randomisation.
To measure the safety of the intervention	Adverse Events relating to the intervention	3-months post randomisation

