7. STUDY SCHEDULE

Visits will be broken up as the participant wishes. The 3-month follow up assessments should be carried out within 2 weeks of completing the intervention, or standard care period where possible.

It is expected that each participant will partake in the study for 10-months in total. 3-months is the end of the intervention period, 6- and 9-months are follow-up.

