8.10 Follow-up assessments

All outcome assessments made at baseline will be repeated at -3, -6 and -9-months post randomisation with the exception of the optional outcome measures which will be performed at baseline and -3 months only.

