11.8 Procedure(s) to account for missing or spurious data

By design there will be no missing data for the minimisation factors, if the primary outcome is missing for less than 5% of the study population at baseline and 3-months, a complete case analysis will be conducted. If there is more than 5% missing outcome data, multiple imputation will be used. The imputation will be carried out using the command MI in Stata. MI replaces missing values with multiple sets of simulated values to complete the data, performs standard analysis on each completed dataset, and adjusts the obtained parameter estimates for missing-data uncertainty using Rubin's rules to combine estimates.

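### Isometric strength at 6 and 9 months is a listed outcome with no assigned analysis, and the regression fixed for outcomes repeated at three visits does not use earlier visits or have a clear missing-data rule

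*Protocol*

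**What the plan says.** All section numbers refer to the STIM-HD randomised trial protocol, not the work package 1 protocol that precedes it.

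- **Timepoints.** Section 3.4 gives isometric strength, in the row for the primary objective, the timepoints "Screening visit (as a familiarisation session), baseline, 3, 6, 9 months post randomisation". The schedules in 7.1 and 7.2 agree, as does 8.10: "All outcome assessments made at baseline will be repeated at -3, -6 and -9-months post randomisation". Section 7 describes the later visits thus: "3-months is the end of the intervention period, 6- and 9-months are follow-up".
- **Primary endpoint.** Section 3.3.1: "The primary outcome is change in muscle strength measured using isometric dynamometry from baseline to 3-months". Section 11.3.3 matches it: "The primary analysis will compare the change in muscle strength from baseline to 3-months (i.e. at the end of the intervention period) between randomised groups". Its model is a linear regression of change on arm, baseline value, age and time on dialysis.
- **Secondary endpoints.** Section 3.3.2 includes hand grip strength and "Isometric rate of force development", but not maximal isometric strength at any visit.
- **Secondary analysis.** Section 11.3.4: "The secondary outcomes will be analysed in a similar manner to the primary outcome". It treats all these outcomes as continuous, specifies linear regression, and does not mention visits or repeated measurement.
- **Missing data.** Section 11.8 applies a complete case analysis "if the primary outcome is missing for less than 5% of the study population at baseline and 3-months" and multiple imputation above 5%. Section 11.3.2 expects losses from death, transplantation and withdrawal. Section 11.1 allows for 10% total attrition.

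**The concern.** Two things are unsettled. First, the sections that define outcomes disagree about 6- and 9-month strength: the table treats it as an outcome of the primary objective, while neither the primary definition nor the secondary list contains it. Depending on which section is followed, a later report could treat these data as part of the primary objective or leave them out. In an open-label trial whose SAP need only be agreed before database lock, the protocol should close that choice.

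Second, most secondary outcomes are measured at three post-baseline visits, but the method fixed for them copies an analysis of one visit. Applied visit by visit, it does not use what is already known about a participant who misses a later visit. The missing-data rule that might make up for this is triggered by the primary outcome at baseline and 3 months, so its reach to 6 and 9 months is unclear. What is at stake is the precision, and under some dropout patterns the accuracy, of the between-arm differences after stimulation has ended.

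**Working it through.** **1. The plan's own figure.** Section 11.1 gives a difference of 21.7 Nm, SD 47.5 Nm, 90% power, 5% significance (two-sided assumed) and 10% attrition. The standardised difference is 21.7/47.5 = 0.457. A two-sample t-test needs 101.7, so 102 per arm; 102/0.9 = 113.3, so 114 per arm and 228 in total. The stated size is reproduced. It is a 3-month calculation, and no attrition figure is given for 6 or 9 months.

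**2. Is 6- and 9-month isometric strength covered?**

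| Section | Includes it? |
|---|---|
| 3.4 table of endpoints/outcomes | Yes, under the primary objective |
| 7.1, 7.2, 8.10 measurement schedule | Yes |
| 3.1 hypotheses, 3.3.1 primary endpoint | No, 3 months only |
| 3.3.2 secondary endpoints | No |
| 11.3.3 primary analysis | No, 3 months only |
| 11.3.4 secondary analysis | No, because it covers secondary outcomes only |

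The data are collected and tabulated as an outcome, but no stated analysis reaches them.

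**3. Precision under random dropout.** Assumptions, none from the protocol: cumulative loss of 10% by 3 months and 25% by 9 months, equal in both arms, and correlation r of 0.6 to 0.85 between visits after baseline adjustment. Take the 3- and 9-month visits and let n be the number randomised per arm. The variance of an arm's 9-month mean is proportional to:

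- available cases only: 1/(0.75n)
- using the 3-month value as well: (1 − r²)/(0.75n) + r²/(0.90n)

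The ratio of the first to the second is 1/(1 − r²/6).

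- r = 0.6: 1/(1 − 0.36/6) = 1.064
- r = 0.85: 1/(1 − 0.7225/6) = 1.137

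Simulation over the same range of correlations gave about 5-14% more variance, which agrees. Since √1.05 = 1.02 and √1.14 = 1.07, confidence intervals would be roughly 2-7% wider.

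**4. Bias under informative dropout.** A simulation of 2,000 trials per setting used 114 per arm, SD of change 47.5 Nm, a true 9-month difference of 10.85 Nm (half the 3-month effect), correlation 0.7 between 3- and 9-month change, and 10%, 20% or 30% loss. All but the SD and the arm size are assumptions. Mean estimated 9-month difference (Nm):

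| Dropout mechanism | Available cases, 10/20/30% loss | Using the 3-month value |
|---|---|---|
| Random | 11.1 / 10.8 / 10.8 | 11.1 / 10.8 / 10.9 |
| Poor 3-month response, equally in both arms | 10.7 / 10.7 / 10.8 | 10.7 / 10.7 / 10.8 |
| Poor 3-month response, NMES arm only (log-odds 1 per SD) | 13.5 / 16.5 / 19.2 | 10.5 / 10.8 / 10.8 |

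Only the third mechanism biases the available-case regression, by about 3 Nm at 10% loss and 8.5 Nm at 30%. Using the 3-month value removes it. In the second mechanism, response is measured from each arm's own mean. If the same rule acted on raw change, the arms would lose different people, because the NMES arm would sit 0.46 SD higher at 3 months. The selection would then again differ by arm, and the available-case difference would be biased, in the opposite direction.

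**The case against.** Several objections carry weight.

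- **The later regressions are not stated to be completers-only.** A reader might infer that each later visit gets its own regression on those still present, but the protocol says neither. Section 11.8 moves to multiple imputation above 5% missing, and the planned 10% attrition exceeds that. An analysis done in the primary's manner could carry imputation with it. This stands. What remains is that the trigger names only the primary outcome at baseline and 3 months, so the extension is not explicit.
- **Later strength does belong to an endpoint table.** A reader might say it belongs to no endpoint at all. Section 3.4 lists it, so the fault is a disagreement between sections.
- **Persistence of benefit is not a stated objective.** The hypotheses concern 3 months, and 14.3 links the 6-month extension to added quality-of-life and fatigue measures. So the documents do not support saying that the trial's main answer on durability is lost. They do still list strength at those visits.
- **Modelling detail belongs in the SAP.** Section 11.3 promises full details there, and the SAP is not at hand. That answers a complaint about silence. It does not answer a mismatch in endpoint definitions, which is a protocol matter, and 11.3.4 is not silent: it names a method.
- **The sizes rest on assumed inputs.** This stands. Dropout after 3 months, its mechanism and the correlations are not in the documents, and a mixed model is one of two good remedies.

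**Conclusion.** The endpoint mismatch is firm: 6- and 9-month isometric strength is listed in 3.4, absent from 3.3.1 and 3.3.2, and reached by neither 11.3.3 nor 11.3.4.

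The modelling point is a worthwhile improvement. The method named in 11.3.4 does not use earlier post-baseline visits, and 11.8 does not clearly extend to later ones. If the regressions are run on available cases, the cost in precision is modest: about 5-14% more variance at 9 months, under assumed 25% loss and correlations of 0.6-0.85. Bias is conditional. It is about zero when dropout is random or selects alike in both arms, and about 3-8.5 Nm in the illustration where only poor NMES responders leave. The documents do not support a claim that the later results will be biased.

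Nothing here affects the 3-month primary endpoint, its analysis or the sample size.

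**What to change.** 1. In 3.3.2, add change in isometric strength from baseline to 6 and to 9 months as a secondary endpoint, and mark the 6- and 9-month entries in the 3.4 strength row as secondary.
2. In 11.3.4, analyse each continuous outcome measured at 3, 6 and 9 months with one repeated-measures model containing visit, arm by visit, baseline by visit and the minimisation factors, with an unstructured covariance. Report the arm difference with a 95% confidence interval at each visit. Alternatively, keep per-visit regressions and extend the multiple imputation in 11.8 to the later visits, with earlier visits in the imputation model.
3. In 11.8, state which missing-data rule governs the 6- and 9-month outcomes.

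The 3-month primary regression stays as written. The cost is protocol and SAP wording and slightly more programming, with no new data, visits or participants.
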